16.1.3. Objective Response Rate

Objective response rate (ORR) is defined as the proportion of patients with a best overall complete response (CR) or partial response (PR) per RECIST V.1.1. To be assigned a status of PR or CR, changes in tumor measurement must be confirmed by repeat assessment performed no less than 4 weeks after the criteria for response are first met. ORR (regardless of confirmation) will also be computed separately, including in the numerator subjects who have CR, unconfirmed CR, PR or unconfirmed PR. The denominator for the calculation of ORR and ORR regardless of confirmation will include all patients in EAS.

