10.2 Analysis Populations

The following analysis populations have been defined for the study:

- Note: the **DLT Evaluable Set** (dose escalation phase) is defined in [Section 5.1.1](#).
- **Safety Analysis Set (SAS) – (All Treated Population):** This population includes all patients who have received at least one dose of surufatinib. Safety data will be evaluated based on this population's outcome. Patients in the SAS will be analyzed by their actual dose initially received. If patients have dose reduction during the study, all data will be summarized/analyzed based on the initial dose of

study drug received. Efficacy endpoints PFS and OS (OS applies to BTC and STS cohorts only) will be analyzed based on this population.

- **Pharmacokinetic Analysis Set (PKAS):** This population will include all patients who received at least one dose of surufatinib and have at least one PK sample obtained and analyzed.
- **Efficacy Analysis Set (EAS):** This population includes all patients who have received at least 1 dose of surufatinib and have had at least 1 post- baseline tumor assessment. All efficacy endpoints will be analyzed will based on this analysis set, except for PFS and OS, which will be analyzed based on SAS.

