6.4. EFFICACY ANALYSIS SET (EAS)

This analysis set includes all patients who have received at least one dose of surufatinib and have had at least one

CCI

post-baseline tumor assessment.

All efficacy endpoints will be analyzed based on this analysis set except for analysis of PFS and OS, which will be analyzed based on the SAS. The OS analysis will be performed for the BTC and STS cohorts only.

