8.2. MISSING DATA

Generally, the missing efficacy and safety data will not be imputed except for the critical missing and incomplete dates which will be handled as described in this section.

CCI

For partially missing dates, the Age (Years), Duration of malignancy (years) and Duration of metastasis (years) will be based on imputed values. For all calculation elements, if the date part is missing while year and month present, 15th of the month will be used for imputation. If both date and month part are missing while year presents, July 1st will be used for imputation.

When no imaging/measurement was done at all at a particular time point, the patient is not evaluable at that time-point. If only a subset of lesion measurements were made at an assessment, usually the case is also considered not evaluable at that timepoint, unless a convincing argument can be made that the contribution of the individual missing lesion(s) would not change the assigned time point response.

For ORR and DCR calculation, patients with missing responses will be considered non-responders, thus contribute only to the denominator.

Initial Diagnosis Date

If year and month are known but the day is unknown, day will be imputed as 15. If only year is known, month and day will be imputed to July 1st. If the diagnosis date is completely missing or the year part is unknown, the diagnosis date will not be imputed. The imputed date will be compared to reference start date. If it is later than the reference start date, the incomplete date will be imputed as the reference start date.

Adverse Events Date

For adverse event, incomplete start dates and/or stop dates will be imputed. Start date will be imputed first when the start date and stop date are both incomplete for a patient. If the field of year is missing, then no value will be imputed. The following rules will be applied to impute the incomplete start date, assuming year is available.

Missing or incomplete start date

In case the start date of an AE is completely missing, or year part is unknown, the start date of AE will not be imputed.

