16.1.2. Best Overall Response

Best overall response (BOR) will be calculated based on the overall visit responses obtained up until RECIST progression is documented, irrespective of whether patients discontinued study medication. In the absence of RECIST progression, BOR is determined by using visit responses up until the last evaluable overall visit response.

Note, CR or PR response(s) after receiving subsequent anti-cancer therapy will not be included.

A patient's overall best objective response will be determined:

- CR: At least one visit response of CR confirmed by subsequent imaging at least 25 days (4 weeks – 3 days window) later with no evidence of progression between confirmation visits. It is required that there is no other overall response, except CR and NE, between the first CR and the subsequent confirming CR which meet the confirmed CR criteria, i.e. CR-NE-CR is the confirmed CR.
- PR: At least one visit response of PR confirmed by subsequent imaging at least 25 days (4 weeks – 3 days window) later with no evidence of progression between confirmation visits. It is required that there is no other overall response, except CR or PR or NE, between the first PR and the subsequent confirming CR or

CCI

PR which meet the confirmed CR or PR criteria, i.e PR-NE-PR is the confirmed PR. If the first PR followed by SD and no matter the requirement of SD is satisfied or not, i.e. PR-SD-PR, the subsequent PR will not be qualified as confirmed PR.

- SD needs to sustain for at least 8 weeks: Stable disease recorded at least 53 days after start of treatment (8 weeks from start of treatment, and also allowing a 3-day visit window). For example, an overall visit response of SD on day 28 will not be considered as SD.
- PD: Progression, or death in the absence of CR/PR or SD.
- NE: No evidence of CR/PR or SD or PD or death.
- Unconfirmed CR: If the BOR is not qualified as confirmed CR or PR but with at least one visit response of CR prior to subsequent new anti-tumor therapy or PD, then it will be considered as unconfirmed CR.
- Unconfirmed PR: If the BOR is not qualified as confirmed CR or PR but with at least one visit response of PR prior to subsequent new anti-tumor therapy or PD, then it will be considered as unconfirmed PR.

In addition, following special scenarios shall be considered for the determination of BOR:

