16.1.4. Disease Control Rate

Disease control rate (DCR) is defined as the proportion of patients whose best overall response from baseline is either CR, PR, or SD per RECIST v.1.1. The denominator for the calculation of DCR will include all patients in EAS subset of response evaluable patients. Response evaluable patients refer to patients with a baseline RECIST assessment.

CCI

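### ORR and DCR leave out treated patients who were never scanned after baseline, so the plan's own missing-response rules cannot count them as failures

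*SAP*

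**What the plan says.** **Set.** Protocol 10.2 defines the EAS: "This population includes all patients who have received at least 1 dose of surufatinib and have had at least 1 post- baseline tumor assessment". SAP 6.4 gives the same definition and adds: "All efficacy endpoints will be analyzed based on this analysis set except for analysis of PFS and OS". PFS and OS use the Safety Analysis Set (SAS), which is everyone who took at least one dose.

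**Denominators.** SAP 16.1.3, on ORR: "The denominator for the calculation of ORR and ORR regardless of confirmation will include all patients in EAS". SAP 16.1.4, on DCR: "The denominator for the calculation of DCR will include all patients in EAS subset of response evaluable patients". Section 16.1.4 explains that response evaluable means having a RECIST assessment at baseline. SAP section 6 defines no such set, and protocol 10.2 makes no separate provision for DCR.

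**Rules for patients without a response.** SAP 8.2: "For ORR and DCR calculation, patients with missing responses will be considered non-responders, thus contribute only to the denominator". SAP 16.1.2 assigns best response as follows: "PD: Progression, or death in the absence of CR/PR or SD". A patient with none of these outcomes is not evaluable.

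**Surrounding provisions.** The first post-baseline scan is on Cycle 2 Day 1 (SAP 16). SAP 4.4, which lists departures from the protocol, mentions only ECG analyses. SAP 16.4 plans no sensitivity or supporting efficacy analysis.

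**The concern.** Whether a treated patient enters the ORR and DCR denominators depends on something that happens after treatment starts: reaching a scan. A patient with no post-baseline scan cannot have a RECIST response or documented stable disease, so everyone removed this way would have counted as a failure.

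SAP 8.2 and 16.1.2 between them already give such a patient a place. A death would be PD, a survivor would be not evaluable, and both would count against the drug. But the EAS definition acts first, so neither rule applies.

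The outcome turns on a few days. A patient with stable disease at the day-29 scan who then withdraws stays in the EAS and is not counted as controlled, because 16.1.2 requires stable disease to be recorded at day 53 or later. A patient who withdraws on day 27 and is never scanned disappears from the calculation.

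ORR and DCR are to be presented together (SAP 16), yet the text allows them different denominators. No all-treated version is planned that would show the size of the effect.

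**Working it through.** **Is there a planned figure to reproduce?** No. The documents give no target ORR or DCR, no sample size based on them, and no expected share of unscanned patients. The decision rules in protocol 10.1 concern PFS rates. They reproduce by exact binomial (Arm A, at least 9 of 30: 90.6% and 2.8%; Arms B and C, at least 6 of 15: 84.9% and 4.9%; each Arm D subtype of 10, at least 3: 83.3% and 7.0%) and do not depend on the ORR or DCR denominator.

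**Formula.** Let n be the number treated, r the number with response (or disease control), and f the share of treated patients with no post-baseline assessment.

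- All-treated rate = r/n
- EAS rate = r/(n(1-f))
- Ratio = 1/(1-f)

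Since f is at least 0, the ratio is at least 1. A rate of zero stays zero.

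**Factor, with f assumed:**

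- f = 0: 1.00
- f = 5%: 1/0.95 = 1.05
- f = 10%: 1/0.90 = 1.11
- f = 15%: 1/0.85 = 1.18
- f = 20%: 1/0.80 = 1.25

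**Illustrations.** Arm sizes are from protocol 10.1. Responder, control and unscanned counts are assumed.

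| Arm | Unscanned | ORR, all treated | ORR, EAS | DCR, all treated | DCR, EAS |
|---|---|---|---|---|---|
| BTC, n = 30 | 3 | 3/30 = 10.0% | 3/27 = 11.1% | 15/30 = 50.0% | 15/27 = 55.6% |
| BTC, n = 30 | 6 | 3/30 = 10.0% | 3/24 = 12.5% | 15/30 = 50.0% | 15/24 = 62.5% |
| NET arm, n = 15 | 2 | 2/15 = 13.3% | 2/13 = 15.4% | 11/15 = 73.3% | 11/13 = 84.6% |
| STS, n = 55 | 6 | 5/55 = 9.1% | 5/49 = 10.2% | 25/55 = 45.5% | 25/49 = 51.0% |

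The 95% Clopper-Pearson interval moves with the estimate. For BTC DCR with 3 unscanned it goes from 31.3-68.7% to 35.3-74.5%. The shift is small against the width of the interval, but it always has the same sign.

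**The DCR subset.** It is at most as large as the EAS, and equals it if every EAS patient has a baseline RECIST assessment. Protocol 6.1 requires measurable disease at entry, so a further loss of 0 or 1 patient per arm is a reasonable guess. It is not a documented figure.

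**The case against.** **The excluded group is narrow.** A reader might infer that early deaths and drop-outs in general leave the denominator. The documents do not support that. Anyone with one post-baseline assessment stays in. Stopping drug for toxicity does not end scanning: protocol 5.5 continues tumor assessments until progression, new therapy or withdrawal of consent. Scans at the treatment completion visit count (SAP 16), and extra scans are allowed when progression is suspected (protocol 8.2.1). Entry requires ECOG 0-1 and expected survival above 12 weeks. What remains is mainly death, consent withdrawal or loss to follow-up before about day 29. This stands.

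**The size is unknown.** A reader might infer that the rates are in fact inflated. The documents show only that they cannot be biased downward; if every treated patient is scanned there is no effect. Protocol 2.3 reports that 15.8% of monotherapy patients had adverse events leading to discontinuation. It gives no timing, and discontinuation is not the same as being unscanned, so it does not estimate f.

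**PFS does not count all of these patients either.** Although PFS uses the SAS, a never-scanned patient who does not die early is censored at first dose (SAP 16.1.1) and adds nothing to the later Kaplan-Meier estimate. Only early deaths are treated differently. This stands.

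**SAP 8.2 can be read as working within the EAS.** It follows text on incomplete imaging, and an EAS patient may have only non-evaluable scans. So 8.2 and the EAS definition are in tension, not in proven contradiction.

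**The exclusions are visible.** SAP 10 tabulates exclusions from each set with reasons and lists them by patient, so a reader could rebuild the all-treated rates. That helps, but a pre-specified result is better than one the reader must reconstruct.

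**The protocol itself chose the EAS, and the endpoints are secondary.** ORR on the EAS follows protocol 10.2 and is not a deviation. There is no hypothesis testing, and no decision rule rests on ORR or DCR. This limits the weight of the point, but does not remove it.

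**Conclusion.** The point holds in limited form. Treated patients never assessed after baseline are outside both the ORR and the DCR denominators, and the rules that would count them as failures cannot reach them. The resulting factor is 1/(1-f): 1.05 to 1.25 for an assumed f of 5% to 20%, and 1.00 if f is zero. The direction follows from the definitions; the size rests entirely on an f that the documents do not give.

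The DCR-only restriction is a separate, minor fault: an undeclared departure from protocol 10.2 that probably affects almost nobody. A reader might take it as a material further shrinkage of the denominator, but the measurable-disease criterion makes that unlikely.

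The primary PFS analysis is unaffected. The change is worth making because it needs no new data and removes a bias that could only favour the drug.

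**What to change.** - Report ORR and DCR on the SAS with one common denominator. Count treated patients with no post-baseline assessment as non-responders and as not controlled. SAP 16.1.2 already supplies their best-response category: PD for a death, not evaluable otherwise.
- Show the protocol-specified EAS result beside it.
- Delete the response-evaluable restriction in SAP 16.1.4.
- Record the departure from protocol 10.2 in SAP 4.4, and edit SAP 6.4, 16, 16.1.3, 16.1.4 and 16.4 to agree.

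**Cost.** SAP wording and a denominator in the programs. The SAS is already built for PFS, OS and safety. The headline rates may be slightly less favourable. The EAS line must stay, because an interim efficacy analysis of the NET cohorts has already been run (SAP 5.2) and the final results need to be comparable with it.

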16.1.4. Disease Control Rate

Disease control rate (DCR) is defined as the proportion of patients whose best overall response from baseline is either CR, PR, or SD per RECIST v.1.1. The denominator for the calculation of DCR will include all patients in EAS subset of response evaluable patients. Response evaluable patients refer to patients with a baseline RECIST assessment.

CCI

16.1.5. Time to Response

Time to response (TTR) is defined as the time between the start date of study medication until first documented response (CR or PR, which is subsequently confirmed) according to RECIST v.1.1. Time to response is only applicable to patients whose BOR is either CR or PR. TTR (months) will be calculated as (First CR/PR date – start date of study medication + 1) / 30.4375.

16.1.6. Duration of Objective Response

Duration of objective response (DoR) is defined as the time from the first time that the objective response reaches CR or PR, whichever comes first, until the occurrence of PD or death (if the death of the patient occurs before recording the PD). If the response is not confirmed, it will not be included. If a patient does not progress (or does not progress before receiving new anti-cancer treatment) following a response, then their duration of response will use the PFS censoring time.

For those patients with confirmed response, the date of response will be the date of first documented response, not the date of confirmatory tumor assessment for that response. The DoR (months) will be calculated as (PD/Death date - First CR/PR date + 1) / 30.4375 when a patient is deemed to experience a PFS event after first CR/PR, or calculated as (PFS censoring date - First CR/PR date +1)/30.4375 when a patient is deemed to be censored.

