16.1. EFFICACY VARIABLE(S) & DERIVATION(S)

16.1.1. Progression-Free Survival

Progression-free survival (PFS) is defined as the time (in months) from the start date of study medication (Day 1) until the date of objective disease progression as defined by RECIST Version 1.1 or death (by any cause in the absence of progression), whichever occurred earlier.

The PFS time will always be derived based on scan/assessment dates and not based on visit dates. RECIST

CCI

assessments/scans contributing towards a particular visit, which consists of assessment for “Non-Target lesions”, “Target lesions”, and “New lesions”, may be performed on different dates. The following rules will be applied:

- Date of progression will be determined based on the earliest of the dates of the radiological component that triggered the progression.
- When censoring a patient for PFS the patient will be censored at the latest of the dates contributing to a particular overall visit assessment.

If a patient has not experienced progressive disease (PD) or died before the end of study for any reason, progression-free survival will be censored at the date of the last evaluable tumor assessment on or prior to the PD, which is not necessarily confirmed.

Three additional rules apply to PFS only:

[figure not shown]
- If a patient misses two or more consecutive tumor assessment visits, and showed PD or death afterwards, PFS will be censored at the date of last tumor assessment prior to the consecutive missed visits. Two consecutive missed/non-evaluable tumor assessment visit window is calculated as $2*(8 \text{ weeks}+1\text{week window time})$, which is 126 days.
- If a patient reports no baseline tumor assessments or has no evaluable tumor assessment visits after the first dose of study medication, PFS will be censored at the start date of study medication unless they die within two consecutive tumor assessments since the first dose of study medication, i.e., PFS=1 day.
- Of note that tumor assessments after the first new anti-cancer treatment (same day inclusive) will be considered inadequate. If a patient starts new anti-tumor therapy initiated prior to documented disease progression or death on study, PFS will be censored at the date of the last tumor assessment prior to or on the date of new anti-tumor therapy.

See Table 1 for the detailed information of event/censoring rules for PFS:

Table 1: PFS Events/censoring rules

Description	Event/Censor	Date of Event/Censor

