Documented progression before start use of new anti-tumor therapy and no two consecutive missed tumor assessment visits	Event	Date of documented disease progression
Death without progression and without use of new anti-tumor therapy and without missing two consecutive tumor assessment visits	Event	Date of death
Death or progression after two or more consecutive missed tumor assessments	Censor	Date of last evaluable tumor assessment prior to the consecutive missed tumor

CCI

		assessment visits
No evaluable baseline or post-baseline tumor assessment and no new lesion found and no death within two scheduled tumor assessment visits post-baseline	Censor	Date of first dosing of study medication
New anti-tumor therapy started prior to documented disease progression or death on study	Censor	Date of last evaluable tumor assessment before start use of new anti-tumor therapy
No progression and no death before end of study or data cut-off	Censor	Date of last evaluable tumor assessment

Note: Symptomatic deterioration will not be regarded as a progression event.

The PFS will be programmatically derived as follows:

1. If a patient had disease progression or death, then

$PFS \text{ (month)} = ([\text{date of earliest evidence of disease progression or death (including death from any cause)} - \text{start date of study medication}] + 1) / 30.4375$; Otherwise,

2. If the patient was known to have developed one of above censoring criteria, then the PFS is censored and

$PFS \text{ (month)} = ([\text{date of censoring} - \text{start date of study medication}] + 1) / 30.4375$.

3. Special scenario such as two or more consecutive missing tumor assessment visits or new anti-cancer treatment will be handled according to the rules provided in Table 1.

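### SAP 16.1.6 gives conflicting censoring rules for duration of response; under its formula, a responder with an earlier scan gap who later progresses or dies can get a negative or one-day duration

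*SAP*

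**What the plan says.** Four rules in the SAP meet here.

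- **Start of response (16.1.6).** For a confirmed response, "the date of response will be the date of first documented response, not the date of confirmatory tumor assessment".
- **End of response, prose (16.1.6).** DoR runs to PD or death. The PFS censoring time is used "If a patient does not progress (or does not progress before receiving new anti-cancer treatment) following a response".
- **End of response, formula (16.1.6).** The PD or death date is used "when a patient is deemed to experience a PFS event after first CR/PR". Otherwise DoR is "calculated as (PFS censoring date - First CR/PR date +1)/30.4375 when a patient is deemed to be censored".
- **Missed visits (16.1.1 and Table 1).** "If a patient misses two or more consecutive tumor assessment visits, and showed PD or death afterwards, PFS will be censored". The censoring date is that of the last assessment before the gap. In Table 1, progression is an event under this description: "Documented progression before start use of new anti-tumor therapy and no two consecutive missed tumor assessment visits". The row for death carries the same condition, and a separate row censors PD or death that follows such a gap.

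Best overall response (16.1.2) "will be calculated based on the overall visit responses obtained up until RECIST progression is documented". It has no missed-visit rule, and it allows non-evaluable visits between a response and its confirmation.

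Protocol 10.6.2 defines DoR as running to PD or death and gives no censoring rule of its own.

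**The concern.** The missed-visit rule does not require the gap to come immediately before the event, or after the response. A patient can therefore have a gap, resume scanning, show a confirmed response and then progress. Read literally, PFS is censored before the gap, while the response still counts for BOR and ORR. The 16.1.6 formula then subtracts the response date from an earlier censoring date.

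A negative time cannot enter the Kaplan-Meier analysis of DoR planned in SAP 16.2, and the SAP sets no lower limit and no separate DoR censoring rule. If the gap lies between the first PR and its confirmation, the result is positive but wrong, and a check for negative times would not find it. In both cases a documented progression is lost as a DoR event.

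The prose and the formula give such a patient different answers, so the programmer would have to choose, possibly with the data in view. Arms B and C plan at least 15 patients each and most sarcoma subtypes 10 (protocol 10.1), so one responder can matter. SAP 16.4 plans no sensitivity analysis that would show the problem.

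**Working it through.** **Inputs**

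- Scan days: SAP 16 places scans on Day 1 of Cycle 2 and of every second cycle after that. With 28-day cycles these are Days 29, 85, 141, 197, 253 and 309.
- Missed-visit window: SAP 16.1.1 states 126 days. This reproduces: 2 × (56 + 7) = 126.
- Confirmation: a second scan at least 25 days after the first response, with non-evaluable visits allowed in between (SAP 16.1.2).
- Month length: 30.4375 days.

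**Case 1: gap before first response.** SD Day 29; Days 85 and 141 missed; PR Day 197; PR Day 253; PD Day 309.

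1. Confirmation: 253 - 197 = 56 days, so BOR is a confirmed PR dated Day 197.
2. Gap: 197 - 29 = 168 days, which exceeds 126. PD follows, so PFS is censored at Day 29.
3. DoR by the formula: (29 - 197 + 1)/30.4375 = -167/30.4375 = **-5.49 months, censored**.
4. DoR by the prose, since the patient progresses after response without new therapy: (309 - 197 + 1)/30.4375 = 113/30.4375 = **3.71 months, event**.

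**Case 2: gap between first PR and its confirmation.** PR Day 85; Days 141 and 197 non-evaluable; PR Day 253; PD Day 309.

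1. Confirmation: 253 - 85 = 168 days with only non-evaluable visits between, so BOR is a confirmed PR dated Day 85.
2. The same 168 days exceed 126, so PFS is censored at Day 85.
3. DoR by the formula: (85 - 85 + 1)/30.4375 = 1/30.4375 = **0.03 months (one day), censored**.
4. DoR by the prose: (309 - 85 + 1)/30.4375 = 225/30.4375 = **7.39 months, event**.

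**Ordinary censoring.** PR from Day 85, no PD or death, last evaluable scan Day 253: (253 - 85 + 1)/30.4375 = 5.55 months. Where new therapy starts first, responses after it do not count (SAP 16.1.2), so the last scan before therapy is not earlier than the confirming scan. DoR is positive on both routes.

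**All patterns.** The formula was applied to every sequence of SD, PR, non-evaluable and PD over 2 to 7 nominal visits that contains a confirmed PR: 2,168 sequences. If a gap started at the first post-baseline scan, censoring was taken at Day 1 (an assumption).

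| Reading of the missed-visit rule | Negative DoR |
|---|---|
| Any gap of two or more visits before PD (as written) | 44 |
| Only a gap immediately before PD | 0 |

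All 44 end in PD. Death was not enumerated, but the same rule applies to it. The counts show what the rules allow, not how often it would happen.

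**The case against.** The strongest reply is that the SAP already contains the right answer. The 16.1.6 prose, like protocol 10.6.2, ends DoR at PD or death, so in Case 1 it gives 3.71 months with an event. This stands: a reader might infer that -5.49 months is the SAP's single answer, and it is not. The closing formula in the same section does give it, however, and nothing says which sentence governs.

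A second reply is that the 126-day window may be meant to be measured back from the event. In Case 1, PD on Day 309 is only 56 days after the evaluable scan on Day 253, so censoring would not be triggered and the negative value would vanish. That may be what the sponsor intends, but neither 16.1.1 nor Table 1 says so.

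Third, the stakes are limited. DoR is secondary, there is no formal hypothesis testing (SAP 7.6), and DoR may only be listed if responders are few (SAP 16.2). This stands. A listing would expose a negative value, but the one-day value in Case 2 would look plausible.

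**Conclusion.** The point holds as an internal contradiction in 16.1.6, combined with a missed-visit rule in 16.1.1 and Table 1 that, as written, is not tied to the event. Under the formula, an affected responder gets an invalid value (-5.49 months instead of 3.71 with an event) or a wrong one (0.03 instead of 7.39 with an event). The examples assume nominal scan days and the literal reading of the missed-visit rule.

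Two broader inferences are tempting and not supported.

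- A reader might infer that censored responders in general are at risk. They are not. A negative value needs two or more missed or non-evaluable visits before first response, then a confirmed response, then PD or death. This is probably rare, and the documents give no frequency.
- A reader might infer that response duration would be overstated. The direction is not determined: it depends on the other responders' durations and on how the invalid record is handled, which the SAP does not say.

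The same wording reaches PFS. In Case 1, PFS is censored at 29/30.4375 = 0.95 months, although the later scans show no progression until Day 309 (309/30.4375 = 10.15 months).

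**What to change.** 1. **SAP 16.1.1 and Table 1.** State that the missed-visit rule applies only when the two or more missed or non-evaluable visits immediately precede the PD or death, with no evaluable scan in between. Make the change in the text, in both event rows (progression and death) and in the missed-visit censoring row, so that every patient fits one row.
2. **SAP 16.1.6.** Make prose and formula agree. DoR ends at PD or death unless new anti-tumor therapy started first, or two or more consecutive assessments were missed immediately before the event. In those cases, and where there is no PD or death, censor at the last evaluable scan on or after the first CR/PR and before any new therapy.

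The cost is a few sentences and a small change to both derivations, with no new data. The first step touches the primary endpoint, which should be acknowledged. PFS changes only for patients with an earlier gap that was followed by evaluable scans.
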